3.5. End-of-Study

The End-of-Study is defined as the date of the last visit of the last subject.

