8.9. Withdrawal of Subjects from the Study Procedures

Subjects must be withdrawn from study procedures for any of the following:

- Withdrawal of consent
- The subject is unwilling or unable to comply with the protocol

Other reasons for withdrawal of subjects from study procedures might include:

- At the discretion of the Investigator for medical reasons
- At the discretion of the Investigator or Sponsor for noncompliance
- Significant protocol deviation

All efforts will be made to complete and report the observations as thoroughly as possible up to the date of withdrawal. All information, including the reason for withdrawal from study, must be recorded in the eCRF.

Any subject who withdraws consent to participate in the study will be removed from further treatment and study observation immediately upon the date of request. These subjects should be encouraged to complete the early termination study procedures and observations at the time of withdrawal ([Appendix A](#)) and ideally within 2 weeks from the last dose of Study Drug.

For subjects withdrawn for reasons other than withdrawal of consent every effort should be made to complete the early termination study procedures and observations at the time of withdrawal (see [Appendix A](#)).

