8.10.1. Concomitant Therapy

A concomitant therapy is any non-protocol specified drug or substance (including over-the-counter medications, herbal medications and vitamin supplements) administered between screening and Post-Treatment Evaluation Period.

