9.4.1. Serious Adverse Events

In the interest of subject safety, and in order to fulfill regulatory requirements, all SAEs (regardless of their relationship to Study Drug) should be reported to the Sponsor or designee within 24 hours of the Study Center's first knowledge of the event. The collection of SAEs will begin after the subject signs the informed consent form and stop at the end of the subject's follow-up period which is defined as Study Day 127. When the Investigator is reporting by telephone, it is important to speak to someone in person vs. leaving a message. SAEs should be reported using an electronic SAE submission form whenever possible. In situations where the electronic SAE submission is unavailable, an Initial Serious Adverse Event Form should be completed and a copy should be faxed to the Sponsor or designee. The SAE reporting instruction, including the fax number and email address, for reporting SAEs can be found in the Study Reference Manual for the study.

Detailed information should be actively sought and included on Follow-Up Serious Adverse Event Forms as soon as additional information becomes available. All SAEs will be followed until resolution. SAEs that remain ongoing past the subject's last protocol-specified follow-up visit will be evaluated by the Investigator and Sponsor. If the Investigator and Sponsor agree the subject's condition is unlikely to resolve, the Investigator and Sponsor will determine the follow-up requirement.

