9.4.2. Non-Serious Adverse Events

The recording of non-serious AEs will begin after the subject signs the informed consent form and will stop at the end of the subject's follow-up period, which is defined as Study Day 127 / Week 19. The Investigator will monitor each subject closely and record all observed or volunteered AEs on the Adverse Event Case Report Form.

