3.5.3 Exploratory Analyses

The exploratory analyses will be conducted using the PPS and FAS.

The change of the weekly average of at-home BP from Baseline to each schedule post-Baseline visit, and the change and percent change from Baseline to each schedule post-Baseline visit in angiotensin II, renin (Plasma renin activity [PRA]; active renin mass concentration [ARC]), and plasma aldosterone will be compared between ISIS 757456 80 mg group and placebo group. The data will be analyzed in a similar way to the primary analysis. For the at-home BP analysis, subsequent SBP and DBP measurements will be completely removed from this exploratory analysis once the subjects received first administration of antihypertensive therapy during the study.

The percentage of subjects reaching the following goals for the in-clinic BP over time will be summarized, comparison of which will be made between ISIS 757456 80-mg group and placebo group using Fisher's exact test. Subsequent SBP and DBP measurements will be completely removed from this exploratory analysis once the subjects received first administration of antihypertensive therapy during the study.

- Percentage of subjects reaching SBP goal of ≤ 140 mmHg
- Percentage of subjects reaching DBP goal of ≤ 90 mmHg
- Percentage of subjects reaching both goals of SBP ≤ 140 mmHg and DBP ≤ 90 mmHg

The antihypertensive therapy will be identified through medical review when database is locked. The percentage of subjects requiring antihypertensive therapy during the study will be compared between ISIS 757456 80 mg group and placebo group in PPS and FAS using Chi-Square test or Fisher's exact test as appropriate. The time in days from first dose of Study Drug to the first administration of antihypertensive therapy during the study will be summarized using the following descriptive statistics: mean, standard deviation, median, P25, P75, and minimum and maximum. The Kaplan-Meier curves [1] for time to the first administration of antihypertensive therapy will be provided for ISIS 757456 80 mg group and placebo group, comparison of which may be made statistically using the log rank test. The time to the first administration of antihypertensive therapy will be calculated as:

- [Date of the first administration of antihypertensive therapy – Date of first dose of study drug +1]

Patients who did not receive any antihypertensive therapy during the study will be censored at the date of end of study.

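### The censoring date for time to first antihypertensive therapy is defined only at trial level, so subjects who leave the study early would count as event-free after their data stop

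*Combined protocol and SAP*

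**What the plan says.** SAP 3.5.3 measures time to first antihypertensive therapy from the first dose, as "Date of the first administration of antihypertensive therapy – Date of first dose of study drug +1". Kaplan-Meier curves will be provided for each arm, with "comparison of which may be made statistically using the log rank test". The only censoring rule is: "Patients who did not receive any antihypertensive therapy during the study will be censored at the date of end of study". There is no separate rule for withdrawal or loss to follow-up.

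The SAP does not define the end of study. Protocol 3.5 does: "The End-of-Study is defined as the date of the last visit of the last subject". That is one calendar date for the whole trial.

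The protocol describes an individual's end of follow-up in other words. Under 9.4.2, recording of non-serious adverse events "will stop at the end of the subject's follow-up period, which is defined as Study Day 127 / Week 19"; for serious events, 9.4.1 likewise has collection "stop at the end of the subject's follow-up period which is defined as Study Day 127". The glossary treats a subject as on study from consent until that subject's last visit.

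On observation, Protocol 8.9 says that a subject who withdraws consent "will be removed from further treatment and study observation immediately upon the date of request". Concomitant therapy is what is "administered between screening and Post-Treatment Evaluation Period" (8.10.1), and Appendix A collects it at study visits.

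**The concern.** Kaplan-Meier estimation needs each subject to leave the risk set when observation ends. A subject who withdraws consent in the Treatment Period is no longer asked about medication, so a later restart cannot be recorded. If that subject's censoring date is the trial's last visit, or nominal Day 127, the subject still counts in the denominator at every later restart. Unobserved time is then treated as time free of therapy, although SAP 3.3.2 says that missing values are not imputed.

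Two things are at stake. The restart curve is too low in any arm with early study withdrawals. If withdrawal differs between arms, the gap between the curves and the log-rank statistic are distorted as well. The arms are small (about 20 and 10) and withdrawals are not replaced (Protocol 4.3), so one or two subjects matter.

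**Working it through.** The documents give no restart rate, dropout rate or power for this endpoint, so there is no planned figure to reproduce. The counts and rates below are assumptions. From the documents come about 30 subjects randomised 2:1, scheduled follow-up to Day 127, and the two candidate meanings of the censoring date.

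**Step 1: formula.** Let *n* subjects start, *w* leave the study before any restart, and *d* of the remainder restart by Day 127.
- Censoring at own last contact: the risk set is *n − w* at the first restart. The survival factors telescope, and the cumulative restart estimate is *d / (n − w)*.
- Censoring at the trial's last visit or at nominal Day 127: the risk set is *n* at the first restart, and the estimate is *d / n*.

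The second is the crude proportion, which SAP 3.5.3 already compares with a Chi-Square or Fisher's exact test. The relative shortfall is *w / n*.

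**Step 2: worked cases** (withdrawals on Day 20, restarts later).

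| Arm | n | w | d | Own last contact | Late common date |
|---|---|---|---|---|---|
| Placebo | 10 | 2 | 6 | 6/8 = 75% | 6/10 = 60% |
| Placebo | 10 | 3 | 5 | 5/7 = 71% | 5/10 = 50% |
| Active | 20 | 4 | 8 | 8/16 = 50% | 8/20 = 40% |

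For scale, the standard error of the 75% estimate is √(0.75 × 0.25 / 8) = 0.153. The 15-point shift is about one standard error.

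**Step 3: log-rank statistic.** Take 5 active and 4 placebo restarts after Day 64, with withdrawals on Day 43.

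| Withdrawals (active, placebo) | Own last contact: active / placebo, z | Late common date: active / placebo, z |
|---|---|---|
| 0, 0 | 25.0% / 40.0%, −0.88 | 25.0% / 40.0%, −0.88 |
| 4, 2 | 31.2% / 50.0%, −0.94 | 25.0% / 40.0%, −0.88 |
| 4, 1 | 31.2% / 44.4%, −0.70 | 25.0% / 40.0%, −0.88 |
| 1, 3 | 26.3% / 57.1%, −1.54 | 25.0% / 40.0%, −0.88 |

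The late date gives the same answer whoever withdrew. The statistic barely moves with balanced withdrawal, and moves in either direction when withdrawal is unbalanced.

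**Step 4: simulation.** There were 2,000 trials per setting, with 20 active and 10 placebo subjects and a true restart rate of 50% by Day 127 in both arms. Restarts began after Day 43 and withdrawals were spread over Days 20 to 109. Own-last-contact censoring gave 49% to 51% throughout. The late date gave about 46%, 43% and 40% at 10%, 20% and 30% dropout. With 30% dropout on active and 10% on placebo, it gave 39.7% against 46.5%, a false gap of about 7 points, and log-rank rejection was 7.2% against 4.9% under own-contact censoring. With the dropout pattern reversed, it gave 46.9% against 40.6%, but rejection was not raised (4.85% against 5.55%).

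**Step 5: who is affected.** On the nominal schedule (Protocol 3.4.3) a Day 20 withdrawal has had doses on Days 1, 3, 8 and 15, which is four. The Per Protocol Set needs at least five of seven, so withdrawals before the fifth dose (Day 22) affect only the Full Analysis Set, provided the subject has a post-Baseline measurement. Later withdrawals can affect both sets.

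**The case against.** The strongest reply is that the SAP sentence is about individual patients, is in lower case and does not cite Protocol 3.5. It could mean each patient's own end of study, and the glossary's on-study entry supports that. It would also avoid curves running past Day 127. This stands as a reading of intent, and on it there is no error. But the SAP does not say so, and a programmer who looks the term up finds only the trial-level date. Nominal Day 127, the other date a programmer might take from 9.4, over-credits early withdrawals just as much.

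Several stronger inferences are tempting but not supported:
- *All early discontinuers are affected.* Protocol 6.1.4 keeps subjects who stop treatment in the post-treatment evaluations. Only those who leave the study matter, and 8.9 encourages an early termination visit even for them.
- *Placebo subjects with high pressure will drop out unseen.* Under Protocol 8.5.3 and 8.6.5, subjects meeting the confirmed upper-pressure rules may have their medication added back and continue to be followed, so their restarts are observed events. Withdrawal of consent for high pressure remains possible, but the documents give no rate.
- *Completers are biased.* Carrying them past Day 127 lengthens the plotted curve but changes neither the estimate to Day 127 nor the log-rank test, because no later events are recorded.
- *Restarts must cluster after Day 64.* The threshold in 8.5.3 does change then, but Protocol 3.1 and SAP 1.1 give a different home-pressure trigger for the whole Post-Treatment Period. Those passages need reconciling, and the timing of restarts cannot be taken as settled.

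It is also fair that the endpoint is exploratory, the log-rank test optional, and the primary angiotensinogen and secondary blood-pressure analyses untouched.

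**Conclusion.** The point holds on the documents' own definition: the only defined end of study is trial-level, and using it, or nominal Day 127, reduces the Kaplan-Meier estimate to the crude proportion whenever subjects leave before restarts occur. The relative shortfall is up to the fraction withdrawn, for example 60% instead of 75% when 2 of 10 leave early. A between-arm bias needs unequal withdrawal.

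The size rests wholly on assumed withdrawal and restart counts, with withdrawals placed before all restarts in the worked cases, which is close to the worst arrangement. It is zero with no study withdrawals. A reader might infer that the authors deliberately chose a calendar-date rule. The text does not establish that, and confidence about intent should be moderate. This is a clear and cheap correction to one exploratory analysis, with no bearing on the trial's main conclusions.

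**What to change.** Replace the censoring sentence in SAP 3.5.3 with:

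*Subjects who did not receive antihypertensive therapy will be censored at the date of their own last study visit or contact at which concomitant medication was assessed (at latest their Day 127 visit).*

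This settles the meaning under every reading. It costs one SAP sentence and one line of programming, with no change to visits or data collection. The downside is slightly less person-time and, where there are withdrawals, higher restart estimates. The revised rule still assumes, as any Kaplan-Meier analysis does, that leaving the study is unrelated to the need for therapy. Listing study withdrawals by arm, with date and reason, next to the curves would let a reader judge that.

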3.6 Pharmacokinetic Analysis

The plasma pharmacokinetics of ISIS 757456 (as total full-length oligonucleotides or ISIS 757456-equivalent, ISIS 757456-eq.) will be assessed following SC administration(s). The analyses will be conducted on the PK Set.

Metabolite identification and profiling may be determined in some of the collected plasma samples and will be reported separately.

3.6.1 Plasma Concentration Data of Total Full-Length Oligonucleotides

Plasma concentrations of ISIS 757456 (ISIS 757456eq.), along with the scheduled (nominal) and actual samples times (i.e., time from SC dosing) will be listed (when applicable) for each patient, by treatment group, dose cohort, nominal dose, and day. In addition, percent differences between scheduled and actual sampling times will also be listed for all patients. Percent differences between actual administered dose and nominal dose will also be listed.

Plasma concentrations below the lower limit of quantification (LLOQ) will be indicated by "BLQ". For the purpose of calculating typical descriptive statistics (n, mean, SD, %CV, geometric mean, geometric %CV, median, minimum, and maximum) for plasma concentrations, all BLQ values will be set to zero. Mean plasma concentrations that are BLQ will be presented as "BLQ", and the SD and %CV will be reported as not applicable. Summary statistics of the ISIS 757456 plasma concentrations will be tabulated by treatment group, dose cohort, nominal dose, day, and scheduled time point. At the discretion of the pharmacokineticist and/or biostatistician, samples may be excluded from descriptive statistics if there are large deviations between scheduled and actual sampling times, or large deviations between actual dose and nominal dose.

ISIS 757456eq. plasma concentration versus time (actual) profiles for each patient that received ISIS 757456 active treatment, as well as the mean (\pm SD or SE) plasma concentrations versus time (scheduled) profiles, will be presented graphically on linear and semilogarithmic scales. At the discretion of the pharmacokineticist and/or biostatistician, samples may be excluded from the mean plots if there are large deviations between scheduled and actual sampling times.

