3.6.2 Plasma Pharmacokinetic Parameters

The plasma PK of ISIS 757456 (as total full-length oligonucleotides) will be assessed following the first SC dose. Non-compartmental PK analysis of ISIS 757456 (total full-length oligonucleotides) will be carried out on each individual subject data set using Phoenix WinNonlin version 8.0 or higher (Pharsight Corporation, Mountain View, CA). For calculation of PK parameters, all BLQ values will be set to zero. The plasma PK parameters for ISIS 757456eq. will be calculated based on actual sampling times. The plasma PK parameters to be calculated or determined (when applicable) are listed in Table 1. Other plasma PK parameters, as appropriate, may be determined or calculated at the discretion of the PK scientist.

Table 1 Plasma Pharmacokinetic Parameters to be Calculated or Determined

Parameter	Definition/Method	Multiple-dose
		D1
C_{max}	Maximum observed concentration	X
T_{max}	Observed time at which C_{max} occurs	X
T_{last}	Time of last measurable (positive) concentration	X
AUC_{0-t}	Partial AUC: Area under the concentration-time curve from time zero to time t (e.g., t may be 24, 48, 72, or 168 hrs, as applicable), calculated using linear-up log-down method	X
CL_{0-t}/F	Partial clearance divided by F (fraction of the dose absorbed) determined by $Dose/AUC_{0-t}$	X

Note: X designates parameters to be calculated or determined assuming sufficient data

Plasma pharmacokinetic parameters will be summarized using descriptive statistics (n, mean, SD, %CV, geometric mean, geometric %CV, median, minimum, and maximum) by treatment group, dose cohort, nominal dose, and day.

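### Setting BLQ concentrations to zero makes the geometric mean 0 and the geometric %CV undefined at any time point that mixes BLQ and quantifiable values (SAP 3.6.1)

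*Combined protocol and SAP*

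**What the plan says.** SAP 3.6.1 gives one substitution rule for concentrations: "all BLQ values will be set to zero". The rule applies to "typical descriptive statistics (n, mean, SD, %CV, geometric mean, geometric %CV, median, minimum, and maximum) for plasma concentrations". The next sentence holds the only exception: a mean concentration that is itself BLQ is displayed as BLQ, and its SD and %CV are marked not applicable. Geometric statistics are not mentioned there.

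SAP 3.6.2 repeats the rule for derived parameters: "For calculation of PK parameters, all BLQ values will be set to zero". Table 1 of that section has the partial AUC "calculated using linear-up log-down method" and gives example end times: "t may be 24, 48, 72, or 168 hrs, as applicable". Tlast is defined separately as "Time of last measurable (positive) concentration", and the AUC definition does not refer to it. Parameters are planned for Day 1 only, if data suffice.

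**The concern.** The list of statistics and the substitution rule stand in the same sentence of SAP 3.6.1, and they cannot both be applied. A geometric mean exists only for positive values. A literal programmer would report 0 or an error wherever even one subject is BLQ, however many others are well above the limit. A less literal programmer would pick a workaround that nobody pre-specified. At stake is the readability of the planned concentration tables, chiefly any trough or follow-up visit where drug is measurable in some subjects only.

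SAP 3.6.2 raises a related question, because a logarithmic trapezoid also fails when its lower end is zero. A choice made there carries into clearance, defined as dose divided by AUC, and may reach the exposure-response plots of SAP 3.6.3.

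**Working it through.** The documents give no quantification limit, BLQ rate or expected concentration, so there is no plan figure to reproduce. The algebra is exact. The numbers below are illustrations on assumed values.

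**Inputs from the documents.** About 30 subjects (protocol 3.3) at 2:1 (protocol 3.4.3) give 30 × 2/3 = 20 active subjects. The SAP's PK Set contains only subjects who received active drug. Protocol Appendix C has 17 sampling times: five on Day 1 (pre-dose, 1, 2, 4 and 6 h) and one on each of 12 later days. The last is Day 127, which is 127 − 36 = 91 days after the final scheduled dose.

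**Geometric statistics.** Geometric mean = exp(mean of ln C). Geometric %CV = 100 × √(exp(variance of ln C) − 1). If one C is 0, ln C is minus infinity. The mean of the logs is then minus infinity, so the geometric mean is exp(−∞) = 0. The log-scale variance does not exist, so neither does the geometric %CV. The other values do not matter.

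**Illustration.** Assume 20 values at the normal quantiles of a log-normal distribution with geometric mean 10 and nominal geometric CV 60%, so the log-scale SD is √ln(1 + 0.6²) = 0.5545. The lowest value is 10 × exp(−0.5545 × 1.96) = 3.37. Treat the lowest k values as BLQ:

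| k BLQ of 20 | Mean, BLQ = 0 | Median | Geometric mean, BLQ = 0 | Geometric %CV, BLQ = 0 | Geometric mean, quantifiable only | Geometric %CV, quantifiable only |
|---|---|---|---|---|---|---|
| 0 | 11.53 | 10.0 | 10.00 | 59.6 | 10.00 | 59.6 |
| 1 | 11.36 | 10.0 | 0 | undefined | 10.59 | 53.5 |
| 2 | 11.14 | 10.0 | 0 | undefined | 11.10 | 49.7 |
| 5 | 10.25 | 10.0 | 0 | undefined | 12.59 | 42.3 |

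Check for k = 1: the mean falls by 3.37/20 = 0.17, from 11.53 to 11.36. The quantifiable-only geometric mean is exp[(20 ln 10 − ln 3.37)/19] = 10.59.

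**Does the exception help?** It is triggered when the mean is BLQ. In the k = 1 row the mean is 11.36, so it is not triggered. If the word mean is stretched to include the geometric mean, the table shows BLQ beside a mean of 11.36 and a median of 10.0, which misleads.

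**How often could a time point contain a BLQ value?** With independent subjects, the chance of at least one among 20 is 1 − (1 − p)^20. For assumed per-sample BLQ rates p of 1%, 5%, 10% and 20%, it is 18%, 64%, 88% and 99%.

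**AUC.** A rising segment contributes Δt(C1 + C2)/2, and a falling one Δt(C1 − C2)/ln(C1/C2). Assume concentrations 0, 300, 500, 400 and 250 at 0, 1, 2, 4 and 6 h.

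- 0–1 h: 150 (linear).
- 1–2 h: 400 (linear).
- 2–4 h: 2 × 100/ln(500/400) = 896.3.
- 4–6 h: 2 × 150/ln(400/250) = 638.3.
- AUC to 6 h: 2085. The pre-dose zero lies on a rising, linear segment and does no harm.

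The next sample is Day 3 pre-dose, nominally 48 h.

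- If it is 5, the segment is 42 × 245/ln(50) = 2630, and AUC to 48 h is 4715.
- If it is BLQ and set to 0, ln(250/0) does not exist. A linear segment gives 42 × 250/2 = 5250 and a total of 7335. Stopping at Tlast gives 2085.

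The ratio is 7335/2085 = 3.5, and clearance moves by the same factor in the opposite direction.

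**The case against.** The strongest reply is that little depends on these numbers. PK is an exploratory objective. No test or endpoint in the documents uses a geometric mean concentration. The same table shows n, mean, median and range, and individual values are listed with BLQ marked, so a reported zero would be noticed and understood. All of that stands, and it is why the point is minor.

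A reader might infer three stronger things that the documents do not support.

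- **That Day 1 pre-dose is the main casualty.** No drug has been given by then, so all values should be BLQ and zero is a sensible value. The row would already read BLQ with SD and %CV not applicable, and nothing of substance is lost.
- **That zero substitution makes AUC zero or generally undefined.** It does not. The pre-dose zero falls on a linear segment. The log formula fails only on a falling segment that ends in BLQ before the AUC end time, on this schedule mainly 6 h to Day 3 pre-dose. The defect there is a missing rule, and whether any subject would be BLQ by then cannot be known from the documents. Geometric summaries of Cmax or AUC fail only if a subject's own parameter is zero.
- **That late follow-up rows will certainly be blank.** This depends on concentrations and an assay limit that are not given.

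It is also fair to object that quantifiable-only statistics are not neutral. Dropping the lowest values pushes the geometric mean up and tends to shrink its CV, as the table shows. Reporting both as not calculated whenever any value is BLQ would be equally defensible.

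**Conclusion.** The point holds for concentration summaries. At every time point that mixes BLQ and quantifiable values, the SAP's stated rule yields a geometric mean of 0 and no geometric %CV, and its exception does not reach that case. This follows from the formulas and needs no assumption about the assay. How many of the 17 time points would be affected is unknown; the 18% to 99% range rests on assumed BLQ rates of 1% to 20%, about 20 active subjects and independence between them.

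The AUC matter is secondary: a gap in the rules for one kind of segment, worth a factor of 3.5 in an assumed profile and possibly nothing in the real data. Neither issue touches the primary angiotensinogen analysis. Severity is low: a desirable clarification.

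**What to change.** In SAP 3.6.1, keep zero for the arithmetic summaries. Add that the geometric mean and geometric %CV are computed on quantifiable values only and labelled as such, with the number of BLQ values shown beside them, and are reported as not calculated when all values are BLQ. In SAP 3.6.2, state one rule for BLQ values after the peak. For example, treat BLQ after the last quantifiable value as missing, so that AUC stops at Tlast. Leave the pre-dose BLQ at zero.

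The cost is two or three sentences and one extra count in the concentration tables; no new data are needed. The downside is that the quantifiable-only geometric mean is biased upward, and its CV tends to be too small, as the BLQ share rises. In the illustration, 5 BLQ of 20 move them from 10.00 and 59.6% to 12.59 and 42.3%. The displayed count lets the reader see when this matters.
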